#### **7.1.4 Other Procedures**

##### **7.1.4.1 Withdrawal/Discontinuation**

When a subject discontinues/withdraws prior to trial completion, all applicable activities scheduled for the final trial visit should be performed at the time of discontinuation. Any adverse events which are present at the time of discontinuation/withdrawal should be followed in accordance with the safety requirements outlined in Section 7.2 - Assessing and Recording Adverse Events. Subjects who a) attain a CR or b) complete 24 months of treatment with pembrolizumab may discontinue treatment with the option of restarting treatment if they meet the criteria specified in Section 7.1.5.5. After discontinuing treatment following assessment of CR, these subjects should return to the site for a Safety Follow-up Visit (described in Section 7.1.5.3.1) and then proceed to the Follow-Up Period of the study (described in Section 7.1.5.4).

##### **7.1.4.2 Blinding/Unblinding**

Not applicable

#### **7.1.5 Visit Requirements**

Visit requirements are outlined in Section 6.0 - Trial Flow Chart. Specific procedure-related details are provided above in Section 7.1 - Trial Procedures.

##### **7.1.5.1 Safety Follow-Up Visit**

The mandatory Safety Follow-Up Visit should be conducted approximately 30 days after the last dose of trial treatment or before the initiation of a new anti-cancer treatment, whichever comes first. All AEs that occur prior to the Safety Follow-Up Visit should be recorded. Subjects with an AE of Grade > 1 will be followed until the resolution of the AE to Grade 0-1 or until the beginning of a new anti-neoplastic therapy, whichever occurs first. SAEs that occur within 90 days of the end of treatment or before initiation of a new anti-cancer treatment should also be followed and recorded. Subjects who are eligible for retreatment with pembrolizumab (as described in Section 7.1.5.5) may have up to two safety follow-up visits, one after the Treatment Period and one after the Second Course Phase.

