### 5.2.1.2 Dose Modification for Pembrolizumab

Adverse events (both non-serious and serious) associated with pembrolizumab exposure may represent an immunologic etiology. These adverse events may occur shortly after the first dose or several months after the last dose of treatment. Pembrolizumab must be withheld for drug-related toxicities and severe or life-threatening AEs as per 3 below. See Section 5.6 for supportive care guidelines, including use of corticosteroids.

Table 3 Dose Modification Guidelines for Drug-Related Adverse Events

Toxicity	Hold Treatment For Grade	Timing for Restarting Treatment	Treatment Discontinuation
Diarrhea/Colitis	2-3	Toxicity resolves to Grade 0-1	Toxicity does not resolve within 12 weeks of last dose or inability to reduce corticosteroid to 10 mg or less of prednisone or equivalent per day within 12 weeks
	4	Permanently discontinue	Permanently discontinue
AST, ALT, or Increased Bilirubin	2	Toxicity resolves to Grade 0-1	Toxicity does not resolve within 12 weeks of last dose
	3-4	Permanently discontinue (see exception below) a	Permanently discontinue
Type 1 diabetes mellitus (if new onset) or Hyperglycemia	T1DM or 3-4	Hold pembrolizumab for new onset Type 1 diabetes mellitus or Grade 3-4 hyperglycemia associated with evidence of beta cell failure	Resume pembrolizumab when patients are clinically and metabolically stable
Hypophysitis	2-4	Toxicity resolves to Grade 0-1. Therapy with pembrolizumab can be continued while endocrine replacement therapy is instituted	Toxicity does not resolve within 12 weeks of last dose or inability to reduce corticosteroid to 10 mg or less of prednisone or equivalent per day within 12 weeks
Hyperthyroidism	3	Toxicity resolves to Grade 0-1	Toxicity does not resolve within 12 weeks of last dose or inability to reduce corticosteroid to 10 mg or less of prednisone or equivalent per day within 12 weeks
	4	Permanently discontinue	Permanently discontinue
Hypothyroidism		Therapy with pembrolizumab can be continued while thyroid replacement therapy is instituted	Therapy with pembrolizumab can be continued while thyroid replacement therapy is instituted
Infusion Reaction	2 b	Toxicity resolves to Grade 0-1	Permanently discontinue if toxicity develops despite adequate premedication
	3-4	Permanently discontinue	Permanently discontinue

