## 6.0 TRIAL FLOW CHART

### 6.1 Study Flow Chart

Trial Period:	Screening Phase		Treatment Cycles a								End of Treatment	Post-Treatment		
	Pre-screening (Visit 1)	Main Study Screening (Visit 2)	1	2	3	4	To be repeated beyond 8 cycles					Safety Follow-up	Survival Follow-Up	
Treatment Cycle/Title:							5	6	7	8				
Scheduling Window (Days):		-28 to -1		± 3	± 3	± 3	± 3	± 3	± 3	± 3	At time of Discon	30 days post discon	Every 12 weeks	
Administrative Procedures														
Pre-screening Consent	X													
Informed Consent		X												
Inclusion/Exclusion Criteria		X												
Demographics and Medical History	X													
Prior and Concomitant Medication Review	X													
Trial Treatment Administration			X	X	X	X	X	X	X	X				
Post-study anticancer therapy status												X	X	
Survival Status						X					X	X	X	X
Clinical Procedures/Assessments														
Review Adverse Events	X	X	X	X	X	X	X	X	X	X	X	X	X	X
Full Physical Examination		X												
Directed Physical Examination	X		X	X	X	X	X	X	X	X				
Vital Signs and Weight	X	X	X	X	X	X	X	X	X	X				
ECOG Performance Status	X	X	X	X	X	X	X	X	X	X				
Laboratory Procedures/Assessments: analysis performed by LOCAL laboratory														
Pregnancy Test – Urine or Serum β-HCG 	X	X	X	X	X	X	X	X	X	X				
PT/INR and aPTT		X				X					X			
CBC with Differential		X	X	X	X	X	X	X	X	X				

Trial Period:	Screening Phase		Treatment Cycles a							End of Treatment	Post-Treatment		
	Pre-screening (Visit 1)	Main Study Screening (Visit 2)	1	2	3	4	To be repeated beyond 8 cycles				Discon	Safety Follow-up	Survival Follow-Up
Treatment Cycle/Title:							5	6	7	8			
Scheduling Window (Days):		-28 to -1		± 3	± 3	± 3	± 3	± 3	± 3	± 3	At time of Discon	30 days post discon	Every 12 weeks
Comprehensive Serum Chemistry Panel		X	X	X	X	X	X	X	X	X			
Urinalysis		X				X				X			
T3, FT4 and TSH		X				X				X			
Efficacy Measurements													
Tumor Imaging			X		X		X		X		X		
Tumor Biopsies/Archival Tissue Collection/Correlative Studies Blood													
Archival or Newly Obtained Tissue Collection			X			X							
Exploratory Biomarker Blood Collection			X				X				X	X	
Anti-Drug Antibodies and Serum Banking			X	X	X						X		

a only in women of child bearing potential

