## **7.0 TRIAL PROCEDURES**

### **7.1 Trial Procedures**

The Trial Flow Chart - Section 6.0 summarizes the trial procedures to be performed at each visit. Individual trial procedures are described in detail below. It may be necessary to perform these procedures at unscheduled time points if deemed clinically necessary by the investigator.

Furthermore, additional evaluations/testing may be deemed necessary by the Sponsor and/or Merck for reasons related to subject safety. In some cases, such evaluation/testing may be potentially sensitive in nature (e.g., HIV, Hepatitis C, etc.), and thus local regulations may require that additional informed consent be obtained from the subject. In these cases, such evaluations/testing will be performed in accordance with those regulations.

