#### **7.1.1.5.3 Subsequent Anti-Cancer Therapy Status**

The investigator or qualified designee will review all new anti-neoplastic therapy initiated after the last dose of trial treatment. If a subject initiates a new anti-cancer therapy within 30 days after the last dose of trial treatment, the 30day Safety Follow-up visit must occur before the first dose of the new therapy. Once new anti-cancer therapy has been initiated the subject will move into survival follow-up.

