### **7.1.2.4 Vital Signs**

The investigator or qualified designee will take vital signs at screening, prior to the administration of each dose of trial treatment and at treatment discontinuation as specified in

the Trial Flow Chart (Section 6.0). Vital signs should include temperature, pulse, respiratory rate, weight and blood pressure. Height will be measured at screening only.

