#### **7.1.2.5 Eastern Cooperative Oncology Group (ECOG) Performance Scale**

The investigator or qualified designee will assess ECOG status (see Section 11.1) at screening, prior to the administration of each dose of trial treatment and discontinuation of trial treatment as specified in the Trial Flow Chart.

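### CBC and chemistry are not scheduled at discontinuation or at the mandatory 30-day safety visit, so new silent laboratory toxicity before day 30 is found only by discretionary testing

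*Combined protocol and SAP*

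**What the plan says.** The safety visit is mandatory and is to be "conducted approximately 30 days after the last dose of trial treatment or before the initiation of a new anti-cancer treatment, whichever comes first" (Section 7.1.5.1). If new therapy starts within 30 days of the last dose, Section 7.1.1.5.3 adds that the "Safety Follow-up visit must occur before the first dose of the new therapy". Section 7.1.5.1 describes adverse-event recording and follow-up at this visit and names no laboratory test.

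Section 5.6 says that end-of-treatment and follow-up procedures are listed in Section 6 and Section 7.1.5. In Section 6.1 the rows "Comprehensive Serum Chemistry Panel" and "CBC with Differential" are marked at main screening and at Cycles 1 to 8, and nowhere later.

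On late toxicity of pembrolizumab, Section 5.2.1.2 says: "These adverse events may occur shortly after the first dose or several months after the last dose of treatment". Section 7.2 counts an abnormal laboratory finding as an adverse event and requires all adverse events to be reported to 30 days after treatment. Section 7.2.3.2 defines one event of clinical interest purely by AST or ALT, bilirubin and alkaline phosphatase values. It is reportable to 90 days, or to 30 days if new anticancer therapy starts.

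Vital signs are required "prior to the administration of each dose of trial treatment and at treatment discontinuation as specified in" the flow chart (Section 7.1.2.4), and ECOG status "prior to the administration of each dose of trial treatment and discontinuation of trial treatment as specified in the Trial Flow Chart" (Section 7.1.2.5). The chart marks neither at discontinuation.

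**The concern.** The plan expects toxicity after the last dose, treats laboratory abnormalities as adverse events, and brings the patient back at about day 30. Yet it does not schedule the two panels that would show a silent abnormality. A new rise in liver enzymes, glucose or electrolytes, or a fall in blood counts, that starts after the last pre-dose tests and causes no symptoms will be seen only if an investigator decides to test.

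At stake are the patient's safety in that interval and the completeness of the adverse-event table in Section 8.2, which serves the safety objective in Section 3.3. After confirmed progression or new therapy, Section 7.1.5.2 moves the patient to telephone contact. For such patients the 30-day visit is the last scheduled safety visit in person.

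**Working it through.** **1. The chart, row by row.** The labelled columns are 2 screening visits + 8 cycles + discontinuation, 30-day visit and survival follow-up = 13.

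| Row | Marks | Where | Discontinuation | 30-day visit |
|---|---|---|---|---|
| Chemistry | 9 | main screening, Cycles 1-8 | no | no |
| CBC | 9 | main screening, Cycles 1-8 | no | no |
| Vital signs | 10 | both screening visits, Cycles 1-8 | no | no |
| ECOG | 10 | both screening visits, Cycles 1-8 | no | no |
| PT/INR and aPTT | 3 | main screening, Cycle 4, discontinuation | yes | no |
| Tumor imaging | 5 | Cycles 1, 3, 5, 7, discontinuation | yes | no |
| Exploratory blood | 4 | Cycles 1, 5, discontinuation, 30-day visit | yes | yes |

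The chemistry row accounts for every labelled column: 1 empty + 9 marks + 3 empty = 13. CBC, vital signs and ECOG lie in the first part of the chart, where the text as read from the PDF has 14 cells per row, one more than the labels. For CBC this is 1 empty + 9 marks + 4 empty = 14; for the other two it is 10 marks + 4 empty = 14. The marks run without a break from the screening cells to the tenth cell, and everything after is empty. An extra column anywhere to the left would only push discontinuation further from the marks, so the reading stands. Other rows do carry late marks, so no late column has been lost. The PT/INR mark at discontinuation is less certain: the urinalysis and thyroid rows also start with main screening and Cycle 4, but end one cell earlier, at Cycle 8.

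**2. Whether any text fills the gap.**
- Section 7.1.3 times laboratory tests for screening, Second Course entry and before dosing only.
- Section 7.1.4.1 asks at discontinuation for whatever is scheduled for the final visit. CBC and chemistry are not scheduled there.
- Section 7.1.5 refers back to the chart and to Section 7.1.
- Section 7.1.5.1 names no test.

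**3. Age of the last chemistry at the safety visit.** Inputs: sEphB4-HSA on Days 1, 8 and 15 (Section 5.2, Table 2), visit 30 days after the last dose (Section 7.1.5.1), pre-dose tests up to 72 hours = 3 days early (Section 7.1.3). With the last dose on Day 15, the visit falls on Day 15 + 30 = Day 45. Age = 45 − day of last draw.

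- Tests before every dose: 45 − 15 = 30 days; drawn 3 days early, 30 + 3 = 33.
- Tests drawn for the next cycle (Day 22) and that dose withheld: 45 − 22 = 23 days; drawn 3 days early, 23 + 3 = 26.
- Tests on Day 1 only: 45 − 1 = 44 days; drawn 3 days early, 44 + 3 = 47.
- Visit brought forward, assuming for illustration that new therapy starts 14 days after the last dose: visit by Day 15 + 14 = Day 29. With Day-1-only tests, 29 − 1 = 28 days; drawn 3 days early, 28 + 3 = 31.

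Section 7.1.3 wants results reviewed before each dose, and sEphB4-HSA is given weekly, so 23 to 33 days is the better reading. The chart has one column per cycle, so Day-1-only testing remains possible. None of these figures is a ceiling: the visit is only approximately at day 30, and Section 5.2.2 lets Day 1 move by 3 days.

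**The case against.** The strongest reply is that event-driven rules already cover most of this. Adverse events are reviewed at both visits. Events present at discontinuation are followed (Section 7.1.4.1), and those above Grade 1 are followed to Grade 0-1 or until new anti-neoplastic therapy starts (Section 7.1.5.1). Section 7.1 also allows extra testing: "It may be necessary to perform these procedures at unscheduled time points if deemed clinically necessary by the investigator". The liver event of clinical interest expressly accepts unscheduled tests. This stands for known or symptomatic events. It does not reach a new abnormality without symptoms, because nothing prompts the test.

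A second reply is that the remedy does not match the hazard, since late events may come months after the last dose and the liver event is reportable to day 90. This also stands in part: testing at about day 30 leaves days 31 to 90 as they are. It does not remove the case for testing within the 30 days in which all adverse events are reportable.

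A reader might infer more than the documents support:

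- That no blood is taken after treatment. PT/INR and aPTT appear to be marked at discontinuation, and exploratory blood at both visits. These do not replace liver enzymes, glucose, electrolytes or counts.
- That vital signs and ECOG go uncollected at discontinuation. Sections 7.1.2.4 and 7.1.2.5 require both, so a site following the text would collect them; the blank cells are a clerical mismatch.
- That 47 days is the typical or the maximum age. It depends on Day-1-only testing and leaves out the visit and dosing slack.
- That trial conclusions are at risk. The objective response rate rests on imaging. The discontinuation-rate endpoint (Section 4.2.3.1) and the toxicity boundary (Section 8.2) turn on toxicity that stops treatment, or on immune-related toxicity in the first two courses that fails to resolve. Neither depends on a new silent finding after the last dose.

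**Conclusion.** The gap is real and bounded. CBC and chemistry have no scheduled time after the last treatment cycle, and new silent laboratory toxicity between the last pre-dose tests and day 30 depends on discretionary testing. For a visit at day 30 the last chemistry would be roughly 23 to 33 days old with tests before each dose, or about 47 days with Day-1-only tests. These figures assume a last dose on Day 15 and a draw no more than 72 hours before the dose.

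The documents give no rate for such late abnormalities, so no number of missed events can be stated. The effect is on patient safety and on the completeness of a descriptive safety table, not on any decision rule. This is a cheap improvement worth making, not a flaw in the efficacy design.

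**What to change.** In Section 6.1, mark CBC and the chemistry panel:

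- at discontinuation, unless drawn within the preceding 72 hours (the window Section 7.1.3 already uses for pre-dose tests);
- at the 30-day safety visit, including when new therapy brings it forward.

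In the same amendment, mark vital signs and ECOG at discontinuation so that the chart agrees with Sections 7.1.2.4 and 7.1.2.5.

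The cost is a chart amendment and at most 2 × 25 = 50 sets of routine local tests for a full 25-patient cohort over the first treatment period. Since the chart marks exploratory blood at both visits, these are mostly extra tubes and not extra needle sticks. The change covers the period to about day 30. If the sponsor also wants scheduled detection of the liver event to day 90, that needs a separate later test, which this fix does not provide.

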##### **7.1.5.2 Survival Follow-up**

Once a subject experiences confirmed disease progression or starts a new anti-cancer therapy, the subject moves into the survival follow-up phase and should be contacted by telephone

every 12 weeks to assess for survival status until death, withdrawal of consent, or the end of the study, whichever occurs first.

## 7.2 Assessing and Recording Adverse Events

An adverse event is defined as any untoward medical occurrence in a patient or clinical investigation subject administered a pharmaceutical product and which does not necessarily have to have a causal relationship with this treatment. An adverse event can therefore be any unfavorable and unintended sign (including an abnormal laboratory finding, for example), symptom, or disease temporally associated with the use of a medicinal product or protocol-specified procedure, whether or not considered related to the medicinal product or protocol-specified procedure. Any worsening (i.e., any clinically significant adverse change in frequency and/or intensity) of a preexisting condition that is temporally associated with the use of the Vasgene's and/or Merck's product, is also an adverse event.

Changes resulting from normal growth and development that do not vary significantly in frequency or severity from expected levels are not to be considered adverse events. Examples of this may include, but are not limited to, teething, typical crying in infants and children and onset of menses or menopause occurring at a physiologically appropriate time.

Merck product includes any pharmaceutical product, biological product, device, diagnostic agent or protocol-specified procedure, whether investigational (including placebo or active comparator medication) or marketed, manufactured by, licensed by, provided by or distributed by Merck for human use.

Adverse events may occur during the course of the use of Merck product in clinical trials, or as prescribed in clinical practice, from overdose (whether accidental or intentional), from abuse and from withdrawal.

Progression of the cancer under study is not considered an adverse event.

All adverse events that occur after the consent form is signed but before treatment allocation/randomization must be reported by the investigator if they cause the subject to be excluded from the trial, or are the result of a protocol-specified intervention, including but not limited to washout or discontinuation of usual therapy, diet, placebo treatment or a procedure.

From the time of treatment allocation/randomization through 30 days following cessation of treatment, all adverse events must be reported by the investigator. Such events will be recorded at each examination on the Adverse Event case report forms/worksheets. The reporting timeframe for adverse events meeting any serious criteria is described in section 7.2.3.1. The investigator will make every attempt to follow all subjects with non-serious adverse events for outcome.

Adverse events will not be collected for subjects during the pre-screening period

### **7.2.1 Definition of an Overdose for This Protocol and Reporting of Overdose to the Sponsor, Vasgene Therapeutics and to Merck**

For purposes of this trial, an overdose of pembrolizumab will be defined as any dose of 1,000 mg or greater ( $\geq 5$  times the indicated dose). No specific information is available on the treatment of overdose of pembrolizumab. Appropriate supportive treatment should be provided if clinically indicated. In the event of overdose, the subject should be observed closely for signs of toxicity. Appropriate supportive treatment should be provided if clinically indicated.

If an adverse event(s) is associated with (“results from”) the overdose of a Merck product, the adverse event(s) is reported as a serious adverse event, even if no other seriousness criteria are met.

If a dose of Merck’s product meeting the protocol definition of overdose is taken without any associated clinical symptoms or abnormal laboratory results, the overdose is reported as a non-serious Event of Clinical Interest (ECI), using the terminology “accidental or intentional overdose without adverse effect.”

All reports of overdose with and without an adverse event must be reported within 24 hours to the Sponsor, Vasgene Therapeutics and within 2 working days hours to Merck Global Safety. (Attn: Worldwide Product Safety; [contact])

### **7.2.2 Reporting of Pregnancy and Lactation to the Sponsor, Vasgene Therapeutics and to Merck**

Although pregnancy and lactation are not considered adverse events, it is the responsibility of investigators or their designees to report any pregnancy or lactation in a subject (spontaneously reported to them) that occurs during the trial.

Pregnancies and lactations that occur after the consent form is signed but before treatment allocation/randomization must be reported by the investigator if they cause the subject to be excluded from the trial, or are the result of a protocol-specified intervention, including but not limited to washout or discontinuation of usual therapy, diet, placebo treatment or a procedure.

Pregnancies and lactations that occur from the time of treatment allocation/randomization through 120 days following cessation of Sponsor’s product, or 30 days following cessation of treatment if the subject initiates new anticancer therapy, whichever is earlier, must be reported by the investigator. All reported pregnancies must be followed to the completion/termination of the pregnancy. Pregnancy outcomes of spontaneous abortion, missed abortion, benign hydatidiform mole, blighted ovum, fetal death, intrauterine death, miscarriage and stillbirth must be reported as serious events (Important Medical Events). If the pregnancy continues to term, the outcome (health of infant) must also be reported.

Such events must be reported within 24 hours to the Sponsor, Vasgene Therapeutics and within 2 working days to Merck Global Safety. (Attn: Worldwide Product Safety; [contact])

